2.1.1.7 Multiple assessments within visit windows

When there are *multiple assessments* in a particular visit window, the following rules are applied to select one value "representing" the subject in summary statistics in a visit window (SeeTable 2-2).

Novartis	For business use only	Page 16
SAP Amendment 2.0		AIN457AIT01

For baseline assessment definition see in Section 2.1.1.4. For post-baseline visit windows the following applies (unless otherwise specified):

- for *quantitative variables*, the *closest* to the actual visit is chosen (if two assessments have the same distance, then the earlier one will be chosen)
- for *qualitative variables*, the *worst* record is selected. It is noted that in the analyses performed, *worst* case is always well defined (e.g., for urine protein values "+" and "++", the worst case is defined as "++")

in case qualitative variables are based on quantitative variables, e.g. PASI 75 response, the visit will be assigned to the quantitative variable, and this visit will be used for the derived qualitative variable.

Timing of measurement	Type of data	Rule
Baseline	All data	See section 2.1.1.4
Post-baseline efficacy	All data except DLQI, HADS	The measurement closest to the target day will be used. In the event two measurements are taken equally apart (e.g., 1 day before target date and 1 day after), the earlier one will be used.
Post-baseline efficacy	DLQI,HADS	The measurement closest to the target day will be used. In the event two measurements are taken equally apart, the earlier one will be used. If two measurements have been taken on the same day, select the worst.
Post-baseline safety	Summary visit information (e.g. laboratory values, vital signs etc.)	The (non-missing) measurement closest to the target day will be used. In the event two measurements are taken equally apart (e.g., 1 day before target date and 1 day after), the earlier one will be used. If two measurments are taken on the same day then select the first one (using the time). If two measurements are taken on the same date/time then use the first visit number (assuming this is the planned visit).

Table 2-2 Rules for selecting values for analysis

2.2 Analysis sets

The following analysis populations will be defined for statistical analysis.

- All patients: all patients who signed informed consent and entered in the study, including screen failure.
- Full Analysis Set (FAS): all enrolled patients (i.e. patients entered at week 0 visit 3).
- Safety: all enrolled patients included in the FAS population who were given at least one dose of study drug.
- Intent-to-treat (ITT): all patients included in the safety population with at least one post-baseline efficacy assessment and with the Cw6 assessment.
- Per-Protocol (PP): all patients included in the ITT population who completed the study without any major protocol violation.
- Core phase completers set: All patients who completed the Core phase visits (Week 24) are called core phase completer set.

The primary and secondary objectives will be evaluated on the ITT population. A supportive analysis will be done on the PP population.

All safety evaluations will be based on the safety set.

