9.4.3 Handling of missing values/censoring/discontinuations

All attempts will be made to ensure that the database contains full information for all data. For subjects who prematurely discontinue the study for any reason or subjects with missing visits (after baseline), PASI will be imputed using the Last Observation Carried Forward (LOCF) approach. If all PASI post-baseline efficacy values are missing, then these missing values will not be imputed and this subject will be removed from the analysis.

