2.5.1 Primary endpoint

The primary efficacy endpoint is proportion of patients with PASI 90 response after 16 weeks of treatment, defined as the achievement of \ge 90% improvement (reduction) in PASI score after 16 weeks of treatment compared to baseline, and thereafter for up to 72 weeks.

The primary analysis will be based on the ITT population.

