2.5.3 Handling of missing values/censoring/discontinuations

For patients who prematurely discontinue the study for any reason or patients with missing visits (after baseline), PASI will be imputed using the Last Observation Carried Forward (LOCF) approach. Additionaly non-responder imputation (NRI) analysis will be performed on primary endpoint (i.e., PASI 90 response with logistic regression analysis).

Non-responder imputation rule:

Non-responder imputation will be used: Missing values with respect to response variables based on PASI score will be imputed with non-response regardless to the reason for missing data (e.g. premature study discontinuation, missed visit, administrative issues), exceptions will apply to the following:

• If a subject dropped out the study prior to last scheduled visit and being responders consecutively at least for two preceding visits, the subject will be imputed as responder for the last scheduled visit.

• If a subject who was responder at visit x-1 and visit x+1 but has missing data at visit x, then the subject will be imputed for visit x.

The approach describes above will be adopted also for PASI 90 assessement reported in the extension phase.

The LOCF approach, as well as the NRI approach will be performed for drop-outs and patients with missing visits in between, however no imputation will be done on any visits for patients – entered in the extension phase **and** who have completed the study before reaching 72 weeks.

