2.5.4 Supportive analyses

A sensitivity analysis on the primary efficacy variable will be performed considering the patients who prematurely discontinued the study without a 16-week PASI assessment as non-responders. Hence, for this analysis non-responders patients are those who are PASI 90 responders who prematurely discontinued the study without a 16-week PASI assessment.

Summary of the number and percentage (n and %) of responders patients at week 16 will be presented by cohorts for this supportive analysis. Clopper Pearson confidence interval for a proportion will also be provided.

This supportive analysis will be done on the ITT set.

A supportive analysis on the primary efficacy variable will be also provided using prevalence approach (observed data) on ITT set and also using the PP set using both LOCF and NRI imputation method as well as prevalence approach.

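### The non-responder analyses of PASI 90 leave out dosed, Cw6-typed patients with no post-baseline PASI, who meet both non-responder rules

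*SAP*

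**What the plan says.** SAP 2.2 builds the Safety set from enrolled patients "who were given at least one dose of study drug". The ITT set keeps only those Safety patients "with at least one post-baseline efficacy assessment and with the Cw6 assessment". SAP 5.5, Table 1, applies the efficacy condition to PASI: a patient with no valid PASI after baseline is excluded from ITT and PP.

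SAP 2.5.1 states: "The primary analysis will be based on the ITT population". SAP 2.5.3 uses LOCF for missing PASI and adds an NRI analysis of the primary endpoint by logistic regression. There, missing PASI-based responses are "imputed with non-response regardless to the reason for missing data", with two exceptions. No other analysis set is named for NRI.

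SAP 2.5.4 adds a sensitivity analysis "considering the patients who prematurely discontinued the study without a 16-week PASI assessment as non-responders", and then specifies: "This supportive analysis will be done on the ITT set". The other supportive analyses in 2.5.4 use ITT (observed data) or PP, which is a subset of ITT.

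Protocol 9.4.3 says, alongside its LOCF rule, that if every post-baseline PASI is missing, "this subject will be removed from the analysis". SAP 2.7.3 repeats this for the secondary endpoints; SAP 2.5.3 does not repeat it for the primary endpoint.

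**The concern.** LOCF needs a post-baseline value to carry forward, so it cannot handle a patient who has none. A non-responder rule needs no such value. Placing both on the same set gives the non-responder analyses an exclusion that only LOCF requires.

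The exclusion depends on something that happens after the first dose. Each patient removed this way raises the response rate of his or her cohort. The NRI and 2.5.4 analyses are the planned checks on how the LOCF result handles missing outcomes, and for this group they share its blind spot. No other planned PASI analysis recovers these patients.

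**Working it through.** **1. Does such a patient meet the rules?** Take a dosed patient with a Cw6 result who never has a post-baseline PASI.
- Safety set (SAP 2.2): in.
- ITT (SAP 2.2 and 5.5): out.
- NRI rule (SAP 2.5.3): the week-16 response is missing, so non-response. Both exceptions require response observed at other visits, so neither can apply.
- SAP 2.5.4 rule: if the patient discontinued, there is no week-16 PASI, so non-responder.

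The rules classify the patient as a failure, and the analysis set removes the patient before they are applied.

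**2. The plan's own figures.** From Protocol 9.7 and SAP 3: one-sided alpha 0.025, power 80%, margin 12 points, PASI 90 of 80% in Cw6-positive patients, 219 positive and 146 negative. The Cw6-negative rate is not stated; I take 80%, because equality reproduces the sample size.
- Positive n = (1.960 + 0.842)² × (0.16 + 0.16 × 219/146) / 0.12² = 218.03, rounded up to 219, with 146 negative: 365.
- SE at 219/146 = sqrt(0.16/219 + 0.16/146) = 0.0427, giving power of 80.2%.
- Enrolled = 365/0.90 = 405.6, rounded up to 406.

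The sample size reproduces and is not affected by this point.

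**3. How many patients?** The documents give no count. The drop-out allowance is 406 − 365 = 41 by week 16. PASI is taken at every visit from week 1 (Protocol 6.4.1, Table 6-1). If drop-out were spread evenly, 41/16 = 2.6 patients, about 6% of drop-outs, would leave before week 1. That even spread is an assumption.

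**4. Effect per omitted patient.** Take 244 positive and 162 negative treated (406 in all), with 80% response among patients in ITT. Counting one omitted patient as a failure lowers the cohort rate by
- Cw6-negative: 0.80/162 = 0.49 points;
- Cw6-positive: 0.80/244 = 0.33 points.

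Under NRI, other drop-outs also count as failures, so the rate in ITT would be lower and these shifts smaller. At 0.80 × 0.90 = 72% they are 0.72/162 = 0.44 and 0.72/244 = 0.30 points.

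**5. Effect on the difference, positive minus negative.** With eP and eN omitted, the rates over all treated patients are 0.80 × (244 − eP)/244 and 0.80 × (162 − eN)/162. The upper bound is the difference plus 1.96 × the unpooled SE.

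| Omitted POS / NEG | Upper bound, left out | Difference, counted as failures | Upper bound, counted as failures |
|---|---|---|---|
| 0 / 0 | 7.95 | 0.0 | 7.95 |
| 12 / 8 | 8.15 | 0.0 | 8.49 |
| 0 / 2 | 7.98 | 1.0 | 9.02 |
| 0 / 4 | 8.01 | 2.0 | 10.09 |
| 0 / 8 | 8.07 | 4.0 | 12.22 |
| 4 / 0 | 7.97 | −1.3 | 6.71 |

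All entries are percentage points. The omission counts are illustrative.

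**The case against.** Four points on the other side deserve weight.

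- **The omitted group is a small part of the target.** SAP 2.5.4 addresses everyone who discontinued without a week-16 PASI. Those with at least one earlier post-baseline PASI stay in ITT and are counted. Protocol section 6 also asks patients who stop treatment to return for assessments, and one later PASI is enough for ITT. This stands. A reader might infer that the non-responder analyses omit the failures they were written to count. The documents support that only for the few with no post-baseline PASI at all.
- **The direction is not established.** Patients and investigators are blinded to Cw6 (Protocol 3.1), and the plan assumes equal drop-out in the cohorts. A reader might infer that the gap favours the claim of a difference below 12 points. Nothing in the documents puts these losses mainly in the Cw6-negative cohort; if each loss fell there with probability 0.4, eight out of eight would have probability 0.4⁸ = 0.0007.
- **The 12-point test belongs to the LOCF primary analysis (SAP 2.5.2).** SAP 2.5.3 specifies logistic regression for NRI, and the 2.5.4 sensitivity analysis gives counts, percentages and Clopper-Pearson intervals by cohort. This stands, so the margin serves here only as a yardstick.
- **The exclusion is prespecified and disclosed.** SAP 2.3 reports the size of each set and the reasons for exclusion. A reader of the results could see the gap, but a count of exclusions does not replace the analysis that the rules describe.

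**Conclusion.** The inconsistency is real and its likely effect is small. Dosed, typed patients with no post-baseline PASI satisfy both non-responder rules and are missing from both analyses. The cohort response rates in those analyses are overstated by about 0.5 points per omitted Cw6-negative patient and 0.3 points per omitted Cw6-positive patient at 80% response. Balanced omissions leave the difference almost unchanged, and unbalanced ones can move it in either direction. Starting from equal 80% rates, about eight omissions, all Cw6-negative, are needed to bring the upper bound to the margin; fewer would do if the observed difference already favoured the Cw6-positive cohort.

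This rests on an assumed Cw6-negative rate, illustrative omission counts, and SAP 5.5 Table 1 (not the broader code list in Table 2) deciding who leaves ITT. The Cw6 condition in the ITT definition is not at fault, since an untyped patient cannot be placed in a cohort. The finding does not invalidate the LOCF primary analysis.

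**What to change.** State in SAP 2.5.3 and 2.5.4 that the NRI analysis and the sensitivity analysis use all Safety-set patients with a Cw6 result, that those with no post-baseline PASI count as non-responders, and that the number added is reported per cohort. Apply the same denominator to the NRI analyses of PASI response in SAP 2.7.2, so that NRI tables agree with each other. Confine the removal sentence in SAP 2.7.3 to the analyses that need a post-baseline value, and record the departure from Protocol 9.4.3 in SAP section 4. Leave the LOCF primary analysis on its present set.

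No new data are needed. The cost is slightly lower response rates in the affected tables, and an NRI denominator that differs from the LOCF tables and needs a footnote. If no such patients exist, the results are unchanged.

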4.1 Inclusion criteria

Patients eligible for inclusion in this study have to fulfill **all** of the following criteria:

1. Subject must be able to understand and communicate with the investigator and comply with the requirements of the study and must give written, signed and dated informed consent before any study related activity is performed.
2. Men or women at least 18 years of age at time of screening.
3. Diagnosis of moderate to severe chronic plaque-type psoriasis for at least 6 months (including concomitant psoriatic arthritis as per the Classification Criteria for Psoriatic Arthritis criteria [CASPAR]).
4. Moderate to severe psoriasis as defined at enrollment by:
 - PASI score ≥ 10
 - or
 - PASI score > 5 but < 10 and DLQI ≥ 10
5. Patients that are candidates for systemic therapy, whether treatment naïve or after failed response to other systemic therapy (i.e. cyclosporine, methotrexate and PUVA) or to an anti-TNF α (or is intolerant and/or has a contraindication to these).

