5.5.9 Discontinuation of study treatment and premature patient withdrawal

Patients may voluntarily withdraw from the study for any reason at any time. They may be considered withdrawn if they state an intention to withdraw, fail to return for visits, or become lost to follow-up for any other reason.

If premature withdrawal occurs for any reason, the investigator must make every effort to determine the primary reason for a patient's premature withdrawal from the study and record this information.

The investigator should discontinue the investigational treatment for a given patient and/or withdraw the patient from the study if, on balance, he/she believes that continuation would be detrimental to the patient's well-being.

The investigational treatment must be discontinued under the following circumstances:

- Withdrawal of informed consent
- Severe adverse events that, in the opinion of the Investigator, warrant discontinuation
- Pregnancy
- Use of prohibited treatment as per [Table 5-1](#)
- Any other protocol deviation that results in a significant risk to the patient's safety

Patients that do not achieve PASI 50 at week 16 will terminate treatment. For patients who are lost to follow-up (i.e. those patients whose status is unclear because they fail to appear for study visits without stating an intention to withdraw), the investigator should show "due diligence" by documenting the steps taken to contact the patient, e.g. dates of telephone calls, registered letters in the source, etc.

Patients who are prematurely withdrawn from the study will not be replaced by an equal number of newly enrolled patients.

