5.5.12 Early study termination

The study can be terminated at any time for any reason by Novartis. Should this be necessary, the patient should be seen as soon as possible and treated as a prematurely withdrawn patient. The investigator may be informed of additional procedures to be followed in order to ensure that adequate consideration is given to protect the patient's interests. The investigator will be responsible for informing Ethics Committees (ECs) of the early termination of the trial.

The study extension can be terminated by Novartis for any reason after a period of at least 12 weeks. Termination may occur only in selected regions where the drug is commercially available; this decision will be made on a region-by-region basis, as for some regions the study will continue as planned even though secukinumab may have become commercially available.

6 Visit schedule and assessments

Table 6-1 lists all of the assessments and indicates with an "x" when the visits are performed. All data obtained from these assessments must be supported in the patient's source documentation.

Patients should be seen for all visits on the designated day. A time window of ± 2 days for weekly visits and ± 7 days for the monthly visits is allowed.

Patients who discontinue the investigational treatment should also return for the assessments in Table 6-1. If they refuse to return for these assessments or are unable to do so, every effort should be made to contact them or a knowledgeable informant by telephone, reporting it in the source documents.

At a minimum, patients will be contacted for safety evaluations during the 30 days following the last study visit, including a final contact at the 30-day point. Documentation of attempts to contact the patient should be recorded in the source documentation.

Table 6-1: Assessment schedule (core study)

Visit	1	2	3	4	5	6	7	8	9	10	11	12/EoS
Week (relative to baseline)	-4	-2	0 (± 2 days)	1 (± 2 days)	2 (± 2 days)	3 (± 2 days)	4 (± 2 days)	8 (± 7 days)	12 (± 7 days)	16 (± 7 days)	20 (± 7 days)	24 (± 7 days)
Day	-28	-14 to -7	1	7	14	21	28	56	84	112	140	168
Informed consent	X											
Demographic data		X										
Inclusion/Exclusion criteria		X	X									
Smoking history		X										
Medical History		X										
TNF α - 308 polymorphism	X											
Psoriasis: medical history		X										
Previous Psoriasis therapies		X										
Quantiferon TB-Gold (within 3 months)		X										
Physical Examination		X	X	X	X	X	X	X	X	X	X	X

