Height, weight, BMI and waist		X	X							X		X
Vital signs		X	X				X	X	X	X	X	X
PASI		X	X	X	X	X	X	X	X	X	X	X
IGA mod 2011		X	X	X	X	X	X	X	X	X	X	X
Lab assessments: hematology and chemistry ¹		X	X				X	X	X	X	X	X
hsCRP			X							X		X
HCV, HBV* and HIV tests (within 6 months)		X										
Serum pregnancy test		X										
Urinalysis		X								X		X
Secukinumab administration			X	X	X	X	X	X	X	X	X	X
DLQI			X							X		X
HADS			X							X		X
Cw6 centralized determination	X											
ECG (within 6 months)		X										
Chest X-ray (within 6 months)		X										
Study completion												X [^]
Concomitant medication												As needed
Adverse events												As needed
Liver events												As needed

¹Hematology: Hemoglobin, hematocrit, red blood cell count, white blood cell count with differential (e.g. neutrophils, basophils, eosinophils, monocytes, lymphocytes) and platelet count; Chemistry: Albumin, alkaline phosphatase, total bilirubin, bicarbonate/CO₂, calcium, cholesterol, chloride, creatinine, CK, GGT, glucose, LDH, inorganic phosphorus, lipase, amylase, magnesium, potassium, total protein, AST, ALT, sodium, triglycerides, urea/BUN and uric acid.

* Height will be assessed only at screening or at baseline

* HBsAg, HBsAb, HBcAb

[^] End of Study visit for patients not proceeding to the extension treatment period.

Table 6-2 lists all the assessments of the extension phase and indicates with an “x” when the visits are performed.

Patients should be seen for all visits on the designated day but a time window of ± 7 days is allowed.

Table 6-2: Assessment schedule of extension treatment period

Visit	E0*	E1	E2	E3	E4/ End of Extension or PPD
Week (relative to baseline)	24	36	48	60	72
Recommended visit window (days)	±7	±7	± 7	±7	±7
Informed consent	X				
Inclusion/Exclusion criteria	X				
Physical Examination		X	X	X	X
Weight and waist		X	X	X	X
Vital signs		X	X	X	X
PASI		X	X	X	X
IGA mod 2011		X	X	X	X
Lab assessments: hematology and chemistry [†]		X	X	X	X
Urinalysis		X	X	X	X
Secukinumab administration	AS NEEDED				
DLQI			X		X
HADS			X		X
Check self-administration log		X	X	X	X
Dispensing Secukinumab for self-administration at home	X	X	X	X	
Study extension completion					X
Concomitant medication	AS NEEDED				
Adverse events	AS NEEDED				
Liver events	AS NEEDED				

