2.3 Patient disposition, demographics and other baseline characteristics

All data about patient demographics and baseline characteristics, including derived variables, will be summarized by cohort and overall with summary descriptive statistics on the Safety set. Continuous data will be summarized by n, mean, standard deviation, median, first and third quartiles, minimum and maximum. Categorical data will be presented by absolute and relative frequencies (n and %). P-values will also be displayed for both categorical and continuous variables, wherever required.

The number of patients in each analysis populations will be described and the reasons for excluding a patient from any particular population will be provided with the number of protocol violators for each criterion. The difference between cohorts with respect to protocol deviations and reasons for dropout will be examined by summarizing the protocol deviations by cohorts and overall on the all patients. Also, Major protocol deviations by cohorts and overall on the all patients.

Major protocol deviations are the deviations with Protocol Deviation IDs (DVSPID) as INCL01, INCL02, INCL03, INCL04, INCL05, EXCL02, EXCL03, EXCL04, EXCL05, EXCL06, EXCL07, EXCL15, EXCL16, EXCL19, COMD01, COMD02, COMD03, COMD04, COMD05, COMD06, COMD07, COMD08, COMD09, COMD11, COMD14, COMD16, COMD17, COMD18, COMD19, OTH08 and also patient's meeting the below criteria

• No secukinumab administration

- No valid PASI assessment after baseline
- Patient who didn't complete the study
- Patient's without Cw6 assessment.

Note:

- Prior use of prohibited PsO medication without the recommended wash-out period (PD: COMD01, COMD03, COMD05, COMD07, COMD09, COMD11, COMD16, COMD17, COMD18, COMD19).

- Concomitant use of PsO medication (PD: COMD02, COMD04, COMD06, COMD08, COMD10, COMD12, COMD14, COMD17, COMD18, COMD19).

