5.5 Rule of exclusion criteria of analysis sets

Table 1	Protocol deviations that cause natients to be excluded
	I TOTOCOL DEVIATIONS that cause patients to be excluded

Deviation ID	Description of Deviation (DVTERM)	Exclusion in Analyses	Severity code
INCL01	Informed consent missing or not signed prior to initiating study procedures.	EXCLUDE FROM FAS ITT SAF PP	6
INCL02	"Calculated Age" is expected to be equal or greater than 18 years or age is missing.	EXCLUDE FROM PP	4
INCL03A	Date of diagonosis of plaque type psoriasis is missing or difference between date of plaque type psoriasis and date of Visit date at Week 0 is less than 6 months	EXCLUDE FROM PP	4
INCL3B	Subject has psoriatic arthritis however does not satisfy classification criteria as per CASPAR.	EXCLUDE FROM PP	4
INCL04	Patient is a violator if:	EXCLUDE FROM PP	4
	- PASI less than 10		
	- PASI greater than 5 but less than 10 and DLQI less than 10		
INCL05	Patients candidate for systemic therapy, treatment naive or failed response to at least one systemic therapies	EXCLUDE FROM PP	4
EXCL02	Cyclosporine or methotrexate administration within 4 weeks prior to Day 1.	EXCLUDE FROM PP	4
EXCL03	Anti-TNF alpha therapy within timelines depending on drug half-life.	EXCLUDE FROM PP	4
EXCL04	Previous exposure to secukinumab or any other biologic drug targeting IL-17 or the IL-17 receptor	EXCLUDE FROM PP	4
EXCL05	Previous exposure to ustekinumab or any other biologic drug for the treatment of psoriasis that is not anti-TNF alpha therapy.	EXCLUDE FROM PP	4
EXCL06	Intravenous or intramuscular steroids within 2 weeks prior to screening and during screening.	EXCLUDE FROM PP	4
EXCL07	Ongoing use of corticosteroid topical treatments or UV therapy.	EXCLUDE FROM PP	4
EXCL15	Underlying condition that, in the opinion of Investigator, would pose a risk to subject safety or interfere with study evaluation, procedures and completion.	EXCLUDE FROM PP	4
EXCL16	Abnormal laboratory results at screening:	EXCLUDE FROM PP	4

Deviation ID	Description of Deviation (DVTERM)	Exclusion in Analyses	Severity code
	Liver tests: AST, ALT or ALP greater than $2.0 \times ULN$ or total bilirubin greater than $1.5 \times ULN$ (except for subjects with Gilbert Syndrome).		
EXCL19	Subject is currently enrolled in another investigational study.	EXCLUDE FROM PP	4
OTH08	PASI 50 not achieved at Week 16 however patient continued in the study.	EXCLUDE FROM PP	4

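### The per-protocol set for week-16 PASI 90 is partly selected on the week-16 PASI score, and two exclusion rules behind the analysis sets (INCL04 and code 4) are wrong as written

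*SAP*

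**What the plan says.** SAP 2.2 (and Protocol 9.1 in the same terms) defines PP as "all patients included in the ITT population who completed the study without any major protocol violation". SAP 2.5.4 applies that set to the primary variable, week-16 PASI 90, with LOCF, NRI and observed data. The primary analysis is on ITT.

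These rules bear on a patient who does badly at week 16:

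- Protocol 5.5.9: "Patients that do not achieve PASI 50 at week 16 will terminate treatment".
- Protocol Section 6, before Table 6-1: "Patients who discontinue the investigational treatment should also return for the assessments in Table 6-1".
- Protocol Table 6-1, footnote to week 24: "End of Study visit for patients not proceeding to the extension treatment period".
- SAP 2.3 and SAP 5.5 Table 1 make "Patient who didn't complete the study" a major deviation that excludes from PP.
- SAP 5.5 Table 1, OTH08, also excluded from PP: "PASI 50 not achieved at Week 16 however patient continued in the study".

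On baseline severity, Protocol 4.1 criterion 4 admits PASI of 10 or more, or "PASI score > 5 but < 10 and DLQI" of at least 10. INCL04 in SAP 5.5 Table 1 has two lines: PASI below 10 with no DLQI condition, and "PASI greater than 5 but less than 10 and DLQI less than 10".

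On codes, Table 1 gives code 4 to INCL04, OTH08 and non-completion, each excluded from PP only. It gives the same code to patients with no valid post-baseline PASI, who are excluded from ITT and PP. Table 2 lists codes 1, 2, 4 and 5 as ITT exclusions.

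**The concern.** A PP set is meant to show whether the result holds among patients who followed the protocol. Here a patient can follow it exactly, stop treatment at week 16 for lack of response, leave, and be counted as a major violator. What removes that patient is the week-16 score, which is also the endpoint. Because a PASI 50 failure cannot be a PASI 90 responder, every removal made for this reason takes out a non-responder and raises that cohort's PP response rate. If the removals are unbalanced between cohorts, the PP difference moves for a reason unrelated to adherence. PP is the planned supportive look at a non-inferiority conclusion, so agreement between PP and ITT could be misread as robustness.

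The other two points are separate. INCL04 may flag eligible patients as violators. That costs precision and representativeness, but it is a baseline restriction and not the source of the selection. The code 4 entry matters more, because it could extend the PP exclusions to the primary analysis set.

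**Working it through.** **Inputs.** From SAP 2.5.2 and 3: 12-point margin on POS − NEG, one-sided 0.025, 219 POS and 146 NEG evaluable, POS rate 80%. The NEG rate used for planning is not stated as a number; 80% reproduces the stated size. The PASI 50 failure rate is not in the documents and is assumed below.

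**1. The plan's own figure.** SE = √(0.8·0.2/219 + 0.8·0.2/146) = 0.0427. Power = Φ(0.12/0.0427 − 1.96) = 80.2%. 365/0.9 gives 406. Sample size and dropout inflation both reproduce; the fault is in the set definitions.

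**2. Where a week-16 PASI 50 failure ends up.**

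- Leaves before week 24: non-completer, out of PP.
- Continues: OTH08, out of PP.
- Stops treatment but attends to week 24, as Protocol Section 6 asks: in PP if OTH08 means continued treatment, out if it means continued attendance.

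**3. Effect on the PP comparison.** Let f be the share below PASI 50 at week 16 and r the share of those removed from PP. Then

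- PP rate = p/(1 − r·f), and PP n = n(1 − r·f);
- P(upper bound < 12 points) = Φ((0.12 − gap)/SE − 1.96), with unpooled SE.

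Take true rates at the margin, 80% vs 68%, where this chance should be 2.5%. Example with f = 5% POS and 10% NEG, r = 1: POS 0.80/0.95 = 84.2% (n = 208), NEG 0.68/0.90 = 75.6% (n = 131), gap 8.7 points, SE 0.0452, Φ(−1.22) = 11.1%.

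| f, POS/NEG (assumed) | Gap, r = 1 | Chance, r = 1 | Gap, r = 0.5 | Chance, r = 0.5 |
|---|---|---|---|---|
| 5% / 2% | 14.8 | 0.5% | 13.4 | 1.2% |
| 5% / 5% | 12.6 | 1.8% | 12.3 | 2.1% |
| 2% / 5% | 10.1 | 6.2% | 11.1 | 3.9% |
| 5% / 10% | 8.7 | 11.1% | 10.5 | 5.1% |
| 5% / 12% (extreme) | 6.9 | 20.3% | 9.7 | 7.1% |

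A simulation of 400,000 trials with a Wald bound gives 0.6%, 2.1%, 6.7%, 12.2% and 21.7% for r = 1.

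**4. Break-even.** With r = 1 the gap is unchanged when f₂/(1 − f₂) = (0.80/0.68)·f₁/(1 − f₁). For f₁ = 5% this gives f₂ = 5.8%, a ratio of about 1.17. Above it the gap shrinks toward non-inferiority; below it PP is conservative.

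One plausible pattern is that the same share of PASI 90 non-responders fails PASI 50 in both cohorts. At 80% vs 68% the non-responders are 20% and 32%, a ratio of 1.6, past break-even. With that share at 10%, 20% and 30% and all failures removed, the gaps are 11.4, 10.7 and 9.9 points and the chances 3.4%, 4.7% and 6.8%.

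**5. INCL04 against criterion 4.**

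| PASI, DLQI | Eligible | Flagged if either line suffices | Flagged if both lines must hold |
|---|---|---|---|
| 7, 20 | yes | yes (wrong) | no |
| 7, 5 | no | yes | yes |
| 4, 15 | no | yes | no (wrong) |

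Neither reading matches criterion 4.

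**6. Code 4.** Read literally, Table 2 excludes codes 1, 2, 4 and 5 from ITT and codes 1, 2, 4, 5 and 6 from PP. The two sets would then differ by code 6 alone, which Table 1 gives only to INCL01 (consent). Every OTH08, INCL04 and non-completer patient would leave ITT, against SAP 2.2 and Table 1. Code 6 is also inconsistent: Table 1 excludes INCL01 from FAS and ITT, but code 6 is in neither row of Table 2.

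**The case against.** The protocol stops treatment, not participation, and its glossary separates the two. Since Section 6 asks patients off treatment to keep attending, OTH08 makes sense as a deviation only if it means continued treatment. On that reading adherent failures who attend stay in PP as non-responders, and PP loses only true deviators and patients who leave. This is a fair reading, and it is why the half-removal columns are shown. It does not clear the rule: OTH08 does not say which is meant, and failures who leave are still removed because of events after the endpoint was measured.

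PP is also only supportive. ITT is primary, with LOCF, NRI, observed-data and non-responder analyses planned, and SAP 2.3 reports exclusions and deviations by cohort. That stands, and it limits the weight of the point.

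The sizes rest on assumed failure rates. The larger values need Cw6-negative failures at least double those in Cw6-positive patients and removal of all of them. With full removal at 2%/2%, 2%/3% and 3%/4%, the chance is 2.2%, 3.2% and 3.0%, close to nominal. If true rates and failure shares are equal, as Protocol 1.1 expects of response, the difference itself is not biased. This also stands.

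The Table 2 entry looks like a slip that set programming would expose. Probably so, but as written it contradicts SAP 2.2 and has to be corrected.

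**Conclusion.** The concern holds in all three parts.

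- **PP selection.** The set can drop patients because of the score it is meant to analyse. Both cohort rates can only rise from this; the difference may move either way. At the margin, over the assumed splits, the chance of a PP bound below 12 points is 0.5% to 20.3% with full removal and 1.2% to 7.1% with half removal, against 2.5%. It exceeds nominal materially only when Cw6-negative failures clearly outnumber Cw6-positive ones in proportion.
- **INCL04.** It disagrees with inclusion criterion 4 on either reading. The loss is the share enrolled with PASI above 5 and below 10 and DLQI of at least 10, which the documents do not give.
- **Code 4.** Under SAP 2.2 and Table 1 the ITT inference is untouched. Under Table 2 taken literally it is not.

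This should be corrected. It does not invalidate the primary analysis, provided the ITT row of Table 2 is put right.

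**What to change.** 1. For the week-16 analysis, define PP as ITT patients with no major deviation dated on or before the week-16 visit. Do not use OTH08 or non-completion after week 16 to exclude from it, so that PASI 50 failures stay in and count as non-responders. State explicitly how withdrawal before week 16 is handled, since it may also be related to outcome. Protocol 9.1 carries the same definition, so align it or record the departure in SAP Section 4.
2. Restate INCL04 as the complement of criterion 4: violator if PASI is 5 or less, or if PASI is above 5 and below 10 with DLQI below 10.
3. In SAP 5.5, give patients with no valid post-baseline PASI their own code and remove code 4 from the ITT row of Table 2. Reconcile code 6 for FAS and ITT at the same time.

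The cost is SAP rewording and reprogramming of the set flags. No new data are needed and the planned sample size is unchanged. The week-16 PP set becomes slightly larger and less strict.
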